3.2.8 Biomarker Variables

Absolute and percent change from baseline in the following biomarkers will be analyzed.

- Angiotensin converting enzyme (ACE)
- soluble IL-2 receptor (sIL-2R)
- Interleukin 6 (IL-6)
- soluble TNF α (sTNF α)

Biomarker samples will be corrected for biomarker analysis at pre dose (Hour 0), and at 8 hours on Day 1, 24 hours (Day 2), 50 hours (Day 3), 74 hours (Day 4), 170 hours (Week 2, Day 8), 338 hours (Week 3, Day 15), 674 hours (Week 4, Day 29), 1010 hours (Week 6, Day 43), 1346 hours (Week 8, Day 57), and 1682 hours (Week 10, Day 71) post infusion of XTMAB-16 or placebo. All sampling time points after time T refer to time from the start of infusion.

Unless otherwise stated, derivation of biomarker parameters will be the responsibility of Clinical Pharmacology, Modeling and Simulation (CPMS, formerly Quantitative Clinical Development (QCD), Parexel International. The following biomarker parameters, if data permit, will be determined for XTMAB-16 in serum following single IV dose administration:

Table 3 Biomarker Parameters after Single Dose Administration

Parameter	Definition
AUEC	Area under the effect-time curve
E _{max,obs}	Maximum observed effect
t _{E_{max,obs}}	Time to reach maximum observed effect

4 STATISTICAL METHODS

4.1 Data Quality Assurance

All tables, figures and data listings to be included in the report will be independently checked for consistency, integrity and in accordance with standard Parexel procedures.

4.2 General Presentation Considerations

This section is applicable to all non-PK assessments.

TLF outputs will be generated for XTMAB-16 and pooled placebo by the planned treatment duration.

The participants, who received “Placebo” in each cohort, will be pooled into a single placebo group (Pooled Placebo) in each respective part for all summaries and presentation related to safety for this study. The PK outputs will be generated for each XTMAB-16 dose.

‘Baseline’ is defined as the last observed value of the parameter of interest prior to dosing (this includes unscheduled visits) for each XTMAB-16 dose and pooled placebo group. ‘End of Study’ for a participant is defined as the last available post-treatment assessment. ‘Study Day’ will be calculated relative to the date of randomization i.e. Study Day = Assessment Date -Randomization Date + 1.

In case of any unscheduled repeated assessments occurred during the period, the following rule will be applied, unless specified otherwise:

If unscheduled repeated measurement of a specific parameter occurs prior to the first XTMAB-16 administration (Day 1), then the last obtained value prior to dosing will be considered in the descriptive statistics and in the calculation of change from baseline.

If unscheduled repeated measurement of a specific parameter occurs after Day 1 or XTMAB-16 or Placebo administration, then the first (non-missing) value after dosing will be used in descriptive statistics and in the calculation of change from baseline.

All data will be listed according to the number of decimal places presented in the source data with a limitation on maximum of 3 decimal places. Continuous data will be summarized in terms of the mean, standard deviation (SD), median, minimum, maximum and number of observations, unless otherwise stated.

The minimum and maximum will be reported to the same number of decimal places as the raw data recorded in the database. The mean and median will be reported to one more decimal place than the raw data recorded in the database. The SD will be reported to two more decimal places than the raw data recorded in the database. In general, the maximum number of decimal places reported shall be four for any summary statistic.

Departure from these general rules will be specified in the output shell document.

Categorical data will be summarized in terms of the number of participants providing data at the relevant time point (n), frequency counts and percentages. Any planned collapsing of categories will be detailed in the SAP text and the data displays.

Percentages will be presented to one decimal place. Percentages as “0.0” will be presented for zero counts. Percentages will be calculated using n as the denominator. If sample sizes are small, the data displays will show the percentages, but any textual report will describe frequencies only.

Changes from baseline in categorical data will be summarized using shift tables where appropriate. Confidence intervals will be presented to same decimal place as of associated estimate.

4.3 Software

All report outputs will be produced using [SAS® version 9.4](#) or a later version in a secure and validated environment.

PK analyses will be produced using [Phoenix® WinNonLin](#) version 8.2 or a later version in a secure and validated environment.

All report outputs will be provided to the Sponsor in Microsoft Word document/RTF format.

4.4 Study Participants

4.4.1 Disposition of Participants

A clear accounting of the disposition of all participants who entered into the study will be provided, from screening to study completion.

The participant disposition summaries may include the following:

- A summary of the number of participants screened for entry into the study and the number and percentage of screened failure participants, number and percentage of participants randomized and dosed will be presented for all screened population by XTMAB-16 dose/ pooled placebo group and overall.
- All screened failure participants who did not meet the inclusion criteria and participants who did meet the exclusion criteria will be listed.
- The number and percentage of participants who completed the trial and those who discontinued study (including reasons for early withdrawal) will be presented by XTMAB-16 dose / pooled placebo group for all randomized set.
- Participant disposition will be listed for each participant, including the participant completion status, reason of discontinuation, date of discontinuation on all randomized population set.
- A randomization listing will be presented and include the following: each participant’s randomization number, the participant’s full Screening number, the treatment to which the participant has been randomized and the location of the clinical unit.

Primary reason of study discontinuation, as recorded on eCRF will be presented as one of the following:

- Adverse Event
- Death
- Loss to Follow-up
- Protocol Violation
- Participant withdrew at own request
- Other

4.4.2 Protocol Deviations

Protocol deviations defined as those deviations from the clinical study protocol relating to a participant likely to have an impact on the perceived pharmacokinetic, pharmacodynamic and safety of study treatments and include the following:

- Inclusion/exclusion criteria deviations
- Dosing deviations (e.g., incorrect treatment received, participant was not fasted as per the protocol requirements prior to and after dosing).
- Time window deviations for safety.
- Participants receiving prohibited concomitant medications.
- Sample processing
- Other procedural and study conduct deviations recorded by the Clinical Unit on a protocol deviation log.

Protocol deviations that may potentially impact PK parameter derivations include, but are not limited to:

- More than three emetic episodes and the volunteer was not discontinued
- Missed PK samples that are evaluated to impact estimation of PK parameter(s)
- Time window deviation for PK samplings that may impact the estimation of PK parameter(s).
- Concomitant medications not authorized by protocol (drugs of abuse)

The criteria for the assessment and reporting of protocol deviations will be stipulated in a separate study specific protocol deviation specification (PDS) document. This will include a Windows Allowance Document (WAD) which stipulates tolerance windows for safety and PK assessments. Measurements performed within these tolerance windows will not be considered as protocol deviations and will not be reported as such.

All protocol deviations will be discussed at the data review meeting prior to final database hard lock in order to define the analysis population for the study. Prior to database lock, protocol deviation and analysis population outputs will be produced and will be sent to Sponsor for review. Analysis population classifications will be discussed in Data Review Meeting to discuss the outputs and to decide which participants and/or participant data will be excluded from certain analyses.

Protocol Deviation will be classified as Major/Minor. Minor deviations are defined as those that deviate from accepted procedures that will not adversely affect subject/data, but should be dealt with appropriately. Major deviations are defined as those that deviate from the protocol that are likely to have an impact on the participants rights, safety, well-being, and/or on the validity of the data for analysis.

Important protocol deviations are a subset of protocol deviations that may significantly impact the completeness, accuracy, and/or reliability of the study data or that may significantly affect a participant's rights, safety, or well-being. Important protocol deviations will be reviewed as part of the ongoing data cleaning process and data evaluation. All important deviations will be identified and documented prior to unblinding to confirm exclusion from analysis sets.

All protocol deviations will be listed by participant on all full analysis sets. Protocol Deviations related to COVID-19 will be listed separately.

4.5 Analysis Sets

Following analysis, sets are defined in this study.

Enrolled Set (ES): The ES will consist of all participants who have given informed consent.

Full Analysis Set (FAS): The FAS will consist of all participants randomized into the study. Participants in this analysis set will be used for analyzing demographics and other baseline characteristics.

Safety Set: The safety analysis set will consist of all participants who are randomized to treatment and have received 1 dose of study drug. Participants in this analysis set will be used for demographics, baseline characteristics, and safety summaries. If all participants in the FAS received actual study drug as randomly assigned, summaries of demographics and baseline characteristics will not be presented for the Safety Set.

Pharmacokinetic Per-Protocol Set (PK-PPS): The PK-PPS set will consist of all participants in the Safety Set who provide at least 1 quantifiable serum XTMAB-16 PK sample post dose without important protocol deviations related to study drug administration that would affect the concentration.

Participants who receive placebo will not be part of the statistical analysis and summary statistics for PK data. PK-PPS will be used to conduct the PK analysis to calculate PK parameters, descriptive summaries of PK parameters, statistical analysis for comparison of PK parameters, and create Tables and Figures. PK-PPS will be finalized after unblinding of the study. Any data excluded will be discussed in the CSR. Any excluded subject must have their concentration and PK parameter data listed only and footnoted with reason of exclusion.

Biomarker Set: All participants without any major deviations related to study drug administration and for whom any biomarker (or effect) data are available will be included in the biomarker analysis. However, subjects being included in this population and having received only placebo will also be included as part of this data set.

A summary of classification to analysis population will be presented in a listing by participant including reason of exclusion on all randomized population set. The number and percentage of participants included in each analysis population will be summarized on all randomized population set by dose cohort/ pooled placebo group and overall.

4.6 Demographics and Baseline Characteristics

Demographic and anthropometric variables (age, sex, ethnicity, race, height, weight and BMI) will be listed by participant. Demographic characteristics (age, sex, ethnicity and race) and anthropometric characteristics (height, weight and BMI) will be summarized by XTMAB-16 dose / pooled placebo group and overall, for all participants in the safety analysis set. The denominator for percentages will be the number of participants in the safety analysis set for each treatment or for all participants as applicable.

Age will be calculated as the number of complete years between a participant's birth date and the date of informed consent.

4.7 Medical History and Concomitant Illnesses

Medical history data will be listed by participant including visit, description of the disease/procedure, Medical Dictionary for Regulatory Activities (MedDRA Version 24.0 or latest) system organ class (SOC), MedDRA preferred term, start date, and stop date (or ongoing if applicable).

4.8 Prior and Concomitant Medications

Prior medications are those that started and stopped prior to the dose of IMP. Concomitant

medications are those taken before or after dosing (including medications that started prior to dosing and continued after) and up to end of trial.

Prior and concomitant medications will be presented based on safety analysis population and will be listed by participant and will include the following information: reported name, preferred term, the route of administration, dose, frequency, start date/time, duration, and indication.

Prior and concomitant medication will be coded according to the World Health Organization Drug Dictionary (WHO-DD) (Version March 1, 2021 B3 or latest) and will be classified by Anatomical Therapeutic Chemical (ATC) categories.

If missing data prevents the medication being classified as prior or concomitant, the medication will be considered as concomitant for the data listings.

Medication start and stop dates will be compared to the date of dose of study medication to allow medications to be classified as either Prior only, or Concomitant only. Medications starting after the completion/withdrawal date will be listed but will not be classified or summarized.

Medications that start and stop prior to the date of dose of study medication will be classified as Prior only. Medications will be classified as Concomitant only if they have a start date before or after the date of dose of study medication and up to end of trial.

If medication start and/or stop dates are missing or partial, the dates will be compared as far as possible with the date of dose of study medication. Medications will be assumed to be Concomitant only, unless there is clear evidence (through comparison of partial dates) to suggest that the medication started prior to the dose of study medication. If there is clear evidence to suggest that the medication stopped prior to the dose of study medication, the medication will be assumed to be Prior only.

4.9 Treatment Exposure

A listing of drug administration will be created and will include the dose cohort, treatment received, date and time of administration, dose (unit), dose form, route of administration.

4.10 Pharmacokinetic Evaluation

4.10.1 Pharmacokinetic Concentrations

Concentration Listings:

Pharmacokinetic concentration data for XTMAB-16, will be listed by treatment and subject for the Safety Set. Concentration listings will include nominal PK sampling time, actual sampling time relative to start of infusion, infusion duration, deviation from start of nominal infusion time, percent deviation from nominal time and concentrations. Serum concentrations below the lower limit of quantification (LLOQ) will be presented as below the limit of quantification (BLQ) in the listings and the LLOQ value presented as a footnote. Missing PK samples will be reported as no sample (NS) and/or not reportable (NR) and considered excluded from PK analysis.

Concentration Summary tables:

Source data as reported from the laboratory will be used for calculation of concentration summary statistics. Tabular summaries for concentration-time data will report N (number of participants who received treatment), n (number of participants with non-missing values), and n(BLQ) (the number of participants with BLQ).

Serum concentrations for XTMAB-16 will be summarized by treatment, and nominal timepoint using the PK-PPS set. The following descriptive statistics will be presented for serum concentrations obtained at each nominal time point: N, n, n(BLQ), arithmetic mean, SD, coefficient of variation (CV%), geometric mean, geometric CV% (calculated as: $gCV\% = \text{SQRT}(es^2 - 1) * 100$; where s is the standard deviation of the log-transformed values), median, minimum and maximum values.

For summary tables, all BLQs will be considered zero, and the number of BLQs and non-BLQs at each scheduled time point will be reported. Summary Statistics will not be calculated if non-BLQ concentrations at a scheduled time point is <3 and will be reported as NC. If for any time point any value is zero in this case Geometric mean and Geometric CV(%) for respective time point will not be calculated and reported as NC.

The rules followed for calculation and presentation of concentration data with regards to the number of decimal places/significant digits for the listings of subject level concentrations and summary tables of concentration are as follows:

Table 4 Rounding Rules for Concentration Listings and Tables

Serum Concentration Listings and Tables	Rounding
Individual concentrations	n s.f. as supplied by bioanalytical laboratory
Minimum and Maximum	n s.f. capped at 4
Mean/SD/Median/Geomean	n+1 s.f. capped at 4
CV%/gCV%	1 d.p.
N/n	Whole number

s f = significant figures, d.p. = decimal place

Concentration Figures:

For arithmetic mean linear/linear graphs, all BLQ values will be substituted with zero for calculation of arithmetic mean and for log/linear graphs the log transformed arithmetic mean will be displayed (this should not include zero).

Individual linear/linear and log/linear graphs all BLQ values will be substituted as follows:

- BLQs at the beginning of a subject profile (ie, before the first incidence of a measurable concentration) will be assigned to zero (except for intravenous administration when these BLQs should not be displayed). When using log/linear scale, these timepoints will be considered missing.
- BLQs at the end of a subject profile (ie, after the last incidence of a measurable concentration) will be set to missing.
- Single BLQs which fall between two measurable concentrations will be set to missing.
- Consecutive BLQs which fall between measurable concentrations will be set to missing. Measurable concentrations after consecutive BLQs will be set to missing.

To visualize subject-level concentrations and the comparison between each cohort, the descriptive PK graphs listed below will be generated.

- Figure xx.1: Individual XTMAB-16 Serum Concentration-Time Profiles (Linear and Semi-Logarithmic Scale), (Safety Set)
- Figure xx.2: Combined Individual XTMAB-16 Serum Concentration-Time Profiles (Linear and Semi-Logarithmic Scale) by Treatment, (Safety Set)
- Figure xx.3: Mean (\pm SD) XTMAB-16 Serum Concentration-Time Profiles (Linear and Semi-Logarithmic Scale) by Treatment, (PK-PPS)

Figures will be generated in black and white or color using unique line style and marker for each plot in the graph. Actual times will be used for individual and combined individual serum concentration-time profiles on Safety Set, and nominal times will be used for mean (\pm SD) serum concentration-time profiles (no SD for semi-logarithm plot) on PK-PPS. All plots will be presented on a linear and semi-logarithm scale.

4.10.2 Pharmacokinetics Parameters

Pharmacokinetic parameters will be calculated by non-compartmental analysis methods from the concentration-time data using Phoenix® WinNonlin® (Version 8.2) or higher following these guidelines:

- Actual sampling times relative to the start of infusion rather than nominal times will be used in the calculation of all derived pharmacokinetic parameters except when parameters are calculated for safety/dose escalation meetings when nominal times may be used to calculate PK parameters.
- There will be no imputation of missing data.
- Handling of BLQ data for the derivation of serum PK Parameters
 - BLQs at the beginning of a subject profile (i.e. before the first incidence of a measurable concentration) will be assigned to zero.
 - BLQs at the end of a subject profile (i.e. after the last incidence of a measurable concentration) will be set to missing.
 - Single BLQs which fall between two measurable concentrations will be set to missing.
 - Consecutive BLQs which fall between measurable concentrations will be set to missing. Measurable concentrations after consecutive BLQs will also be set to missing.

Pharmacokinetic parameters will be estimated according to the guidelines presented in Table 3.

Table 5 Pharmacokinetic Parameter and Estimation

Parameter	Guideline for Derivation
C_{max} , t_{max} , C_T	Obtained directly from the observed concentration-time data.
AUC_{0-t} or AUC_{0-last}	
The AUC from zero time (pre-dose) to the time of last quantifiable concentration will be calculated by a combination of linear and logarithmic trapezoidal methods. Unless specifically requested and justified, the linear up/log down trapezoidal method will be employed.
 
The AUC_{0-t} is the sum of areas up to the time of the last quantifiable sample:
 $AUC_{0-t} = \int_0^t C_{last} * dt$

Parexel International

Parameter	Guideline for Derivation
AUC _{0-inf}	
The area from zero time extrapolated to infinite time will be calculated as follows:
 $AUC_{0-inf} = AUC_{0-t} + \frac{C_{last}}{\lambda_z}$ 
where C_{last} is the last observed quantifiable concentration.

%AUC _{ex}	
The percentage of AUC_{0-inf} obtained by extrapolation will be calculated as follows:
 $\%AUC_{ex} = \frac{AUC_{0-inf} - AUC_{0-t}}{AUC_{0-inf}} \times 100$ 
Unless otherwise determined by PK Scientist's best knowledge and judgment, if the %AUC_{ex} is greater than 30% the value, %AUC_{ex}, and all dependent parameters (ie, AUC_{0-inf}, MRT, Vz and CL) will be flagged in listings and excluded from summary tables and statistical analysis of PK parameters. The reason for exclusion will be listed/footnoted in parameter listings.

λ_z and $t^{1/2}$	
 1. The apparent terminal phase rate-constant (λ_z) will be estimated by linear regression of concentration versus time data presented in a log-linear scale. 2. Data are primarily monotonically decreasing in magnitude and are representative of the actual decline in the log concentration-time curve. 3. Only those data points that are judged to describe the terminal log-linear decline will be used in the regression. 4. A minimum number of three data points in the terminal phase will be used in calculating λ_z with the line of regression starting at any post-C_{max} data point (C_{max} should not be part of the regression slope, if possible). Unless otherwise determined by PK Scientist's best knowledge and judgment, if the adjusted correlation coefficient (R² adjusted) is <0.8, it will be excluded from the summary tables and statistical analysis of PK parameters, and λ_z and all the λ_z dependent parameters (i.e. $t^{1/2}$, AUC_{0-inf}, CL, MRT, and Vz) will also be flagged and excluded from summary tables and statistical analysis. The reason for exclusion will be listed/footnoted in parameter listings. 5. Unless otherwise determined by PK Scientist's best knowledge and judgment, the interval used to determine λ_z should be equal or greater than 1.5-fold the estimated $t^{1/2}$, and if less than 1.5-fold, λ_z will be flagged in listings and excluded from summary tables and statistical analysis of PK parameters. All the derived parameters (i.e. $t^{1/2}$, AUC_{0-inf}, CL, MRT, and Vz) will also be flagged from listings and excluded from statistical analysis of PK parameters. The reason for exclusion will be listed/footnoted in parameter listings. 6. The $t^{1/2}$ will be calculated as follows: $t^{1/2} = \ln 2 / \lambda_z = 0.693 / \lambda_z$ 7. Data points may be dropped from the linear regression if the PK Scientist considers the reported values to be anomalous. Any data points so designated should remain in the listings with a footnote and be identified in the study report with a rationale for exclusion.
CL	
Following IV administration, systemic clearance of drug will be calculated from:
 $CL = \frac{Dose}{AUC_{0-inf}}$
V _z	
Volume of distribution at terminal phase following IV dosing may be calculated from:
 $V_z = \frac{Dose}{\lambda_z \times AUC_{0-inf}} = CL / \lambda_z$
V _{ss}	
Following IV administration, the volume of distribution at steady state of drug will be calculated from:
 $V_{ss} = CL \times MRT_{iv}$
MRT	
Mean residence time of the drug is calculated as:
 $MRT = [AUMC_{0-inf} / AUC_{0-inf} - TI/2]$ 
where AUMC_{0-inf} is area under the serum concentration moment (C · t) versus time curve extrapolated to infinity according to the following equation:
 $AUMC_{0-inf} = AUMC_{0-t} + (Ct \cdot t / \lambda_z + Ct / \lambda_z^2)$ 
TI is the length of infusion

DNC _{max} , DNAUC _{0-last} , DNAUC _{0-inf}	
Dose-normalized C_{max}, AUC_{0-t}, and AUC_{0-inf} calculated as:
 
parameter value/Dose

PK Parameters Listings:

Pharmacokinetic parameters will be listed by treatment and subject for the Safety Set. PK parameters that will be excluded from summary tables and statistical analyses of PK parameters will be flagged and footnoted with reason for exclusion.

PK Parameter Summary Tables:

PK parameters will be provided by CPMS group. Biostatistics group will consider this the PK parameters source data and will use this data without rounding for calculation of PK parameter summary statistics tables.

PK parameters will be summarized by treatment for the PK-PPS.

Tabular summaries for PK parameters will report N (number of participants who received treatment) and n (number of participants with non-missing values).

Descriptive statistics for calculated PK parameters will include: N, n, arithmetic mean, SD, CV%, geometric mean, geometric CV%, median, minimum and maximum values. For t_{max} , only median, minimum and maximum values will be presented. No descriptive statistics will be determined when fewer than three individual PK parameters are available.

The rules followed for presentation of PK parameters data with regards to the number of decimal places/significant digits for the listings of subject level PK parameters and summary tables of PK parameters are as follows:

Table 6 Rounding Rules for PK Parameter Listings and Tables

PK Parameter Listings and Tables	Rounding
Derived Individual parameters	4 s.f.
Directly Derived Individual parameters (C_{max} , C_T)	n s.f. as supplied by the analytical laboratory but not more than 4 s.f.
Minimum and Maximum	4 s.f.
Mean/SD/Median/Geomean	4 s.f.
CV%/gCV%	1 d.p.
Comparative estimates	3 d.p.
CI and other percentages	2 d.p.
p-values	4 d.p.
N/n	Whole number
Exceptions for PK Tables	
t_{max} individuals and min/max	2 d.p.
t_{max} median only	2 d.p.

s.f. = significant figures, d.p. = decimal place

PK Parameter Figures:

The following plots will also be generated:

- Boxplots for dose normalized PK parameters (e.g., C_{max} , AUC_{0-last} , and AUC_{0-inf}) versus treatment

Assessment of Dose Proportionality

- Power Model using ANOVA Method:

An ANOVA of the natural log-transformed PK parameters, ln-transformed dose as a fixed and participant as random effect.

Dose-proportionality based on the power model will be accepted (“not rejected”, in terms of statistical inference) if each of the 95% CIs of the slope of the effect of dose level on each of PK parameters includes 1.

For each of the parameters (C_{max} and AUCs) a plot of the log-transformed PK parameter against the log-transformed dose will be constructed including the fitted line from the linear regression and the line of unity.

Sample SAS Code:

```
ODS OUTPUT lsmeans=lsm estimates=est Diffs=diff1;
```

```
PROC MIXED DATA=PKDATA;
```

```
BY ANALYTE PKPARAM ;
```

```
CLASS SUBJECT;
```

```
MODEL LN_PK= LNDOSE/ddfM=KR;
```

```
RANDOM SUBJECT;
```

```
ESTIMATE "LNDOSE" LNDOSE/CL= 0.05;
```

```
RUN;
```

where:

LN_PK: natural log-transformed PK parameter

LNDOSE: natural log-transformed dose level of <drug>

ANALYTE: analyte (LICO FG-459)

PKPARAM: PK parameter

SUBJECT: participant

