3.2.7 Pharmacokinetic Variables

Blood samples will be collected for XTMAB-16 PK analysis at pre dose (Hour 0), at 1 hour after the start of infusion, immediately after the 2-hour infusion (T; infusion termination), and at 3, 8, 14 hours on Day 1, and at 24 hours (Day 2), 50 hours (Day 3), 74 hours (Day 4), 170 hours (Week 2, Day 8), 338 hours (Week 3, Day 15), 674 hours (Week 4, Day 29), 1010 hours (Week 6, Day 43), 1346 hours (Week 8, Day 57), and 1682 hours (Week 10, Day 71) post infusion of XTMAB-16 or placebo. All sampling time points after time T refer to time from the start of infusion. Acceptable windows for PK sample collection are provided in Window Allowance Document. The exact time of sample collection must be recorded on the eCRF.

Unless otherwise stated, derivation of PK parameters will be the responsibility of Clinical Pharmacology, Modeling and Simulation (CPMS, formerly Quantitative Clinical Development (QCD), Parexel International. If calculable, the PK parameters listed in ([Table 2](#)) will be determined for XTMAB-16 in serum following single IV dose administration:

Table 2 Pharmacokinetic Parameters after Single Dose Administration

Parameter	Definition
C_T	XTMAB-16 serum concentration at the end of drug infusion
C_{max}	Maximum observed serum concentration determined directly from the concentration-time profile
t_{max}	Time of maximum serum concentration determined directly from the concentration-time profile
AUC_{0-inf}	Area under the concentration-time curve from time zero extrapolated to infinity
AUC_{0-last}	Area under the concentration-time curve up to last measurable concentration
λ_z	Terminal elimination rate constant
$t_{1/2}$	Terminal elimination half-life calculated as: $\ln 2/\lambda_z$

Parameter	Definition
CL	Total body clearance calculated as: Dose/AUC _{inf}
V _z	Volume of distribution during the terminal phase calculated as: Dose/($\lambda_z \cdot AUC_{0-\inf}$)
MRT	Mean residence time of the drug in the body
V _{ss}	Steady state volume of distribution following IV dosing calculated as: MRT·CL
DNC _{max} , DNAUC _{0-last} , DNAUC _{0-inf}	Dose-normalized C _{max} , AUC _{0-t} , and AUC _{0-inf}

Additional PK parameters may be calculated if needed.

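### SAP Table 5 is inconsistent about which PK parameters leave the summaries when the terminal phase fails a reliability rule

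*SAP*

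**What the plan says.** SAP section 4.10.2, Table 5, has three rules for an unreliable terminal phase. Each can be overridden by the PK scientist.

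- **Extrapolation above 30%.** The rule applies to the value itself "and all dependent parameters (ie" AUC0-inf and others), and closes: "MRT, Vz and CL) will be flagged in listings and excluded from summary tables and statistical analysis of PK parameters".
- **Adjusted R² below 0.8 (item 4 of the λz row).** λz goes, and the dependent list (t1/2, AUC0-inf, CL and others) ends: "MRT, and Vz) will also be flagged and excluded from summary tables and statistical analysis".
- **Interval below 1.5 half-lives (item 5 of the same row).** For λz: "and if less than 1.5-fold, λ_z will be flagged in listings and excluded from summary tables and statistical analysis of PK parameters". The next sentence lists the derived parameters t1/2, AUC0-inf, CL and others, and ends: "MRT, and Vz) will also be flagged from listings and excluded from statistical analysis of PK parameters".

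Vss is a planned parameter in SAP section 3.2.7: "Steady state volume of distribution following IV dosing calculated as: MRT·CL". Dose-normalized AUC0-inf (DNAUC0-inf) is in the same table and is defined in Table 5 as the parameter value divided by dose. Section 4.10.2 also plans boxplots of the dose-normalized parameters by treatment.

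**The concern.** There are two separate inconsistencies.

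(a) Item 5 gives λz and its derived parameters different scopes. Item 4, directly above it, gives them the same scope. Item 6 defines half-life as ln2/λz, so a half-life is no more reliable than the λz behind it.

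(b) Vss and DNAUC0-inf are built entirely from quantities that the rules reject, plus the dose, but no list names them.

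Protocol section 9.1 rules out hypothesis testing, so the descriptive tables are the main PK result, with 9 active participants per dose. One table could show half-life for more participants than λz, or Vss for a profile whose CL and MRT were rejected. The SAP has one group derive the parameters and another program the tables from that source. A parameter that is not listed can therefore go unflagged without anyone having decided so.

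**Working it through.** **Step 1. Dependencies, from the formulas in SAP Table 5.** AUC0-inf = AUC0-t + Clast/λz; CL = Dose/AUC0-inf; Vz = CL/λz; MRT = AUMC0-inf/AUC0-inf − TI/2; Vss = CL × MRT; DNAUC0-inf = AUC0-inf/Dose; t1/2 = ln2/λz. If λz is unreliable, all seven are affected. If AUC0-inf is rejected, so are CL, Vz, MRT, Vss and DNAUC0-inf.

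**Step 2. Printed lists against the dependencies.**

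| Rule | Named as removed from summary tables | Dependent but not named |
|---|---|---|
| Extrapolation >30% | %AUCex, AUC0-inf, MRT, Vz, CL | Vss, DNAUC0-inf |
| Adjusted R² <0.8 | λz, t1/2, AUC0-inf, CL, MRT, Vz | Vss, DNAUC0-inf |
| Interval <1.5 × t1/2 | λz only | t1/2, AUC0-inf, CL, MRT, Vz, Vss, DNAUC0-inf |

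For statistical analysis, as distinct from tables, the interval rule omits only Vss and DNAUC0-inf.

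**Step 3. When the rules apply.** Assumptions: mono-exponential decline, the last three quantifiable samples in the regression, and a half-life of 226.9 h (mouse, 10 mg/kg) to 335.1 h (the human infliximab figure), both from Protocol section 2.2.4. Sampling times are those in SAP section 3.2.7. I use the SAP's 30% limit; Protocol Table 5 prints 20% for AUC0-inf, which is a separate matter. Extrapolated share = 2^(−tlast/t1/2).

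| Last quantifiable sample | Extrapolated share | Three-point interval, in half-lives |
|---|---|---|
| 338 h | 36% to 50% | 264 h: 1.16 to 0.79 |
| 674 h | 13% to 25% | 504 h: 2.22 to 1.50 |
| 1682 h | 0.6% to 3.1% | 672 h: 2.96 to 2.01 |

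- At 338 h both rules apply. The extrapolation rule removes AUC0-inf, CL, MRT and Vz, so of the parameters listed in item 5 only half-life stays in the tables.
- At 674 h and beyond neither rule applies in this range, though narrowly at 335.1 h (504/335.1 = 1.504).
- For CL to stay in the tables, item 5 must apply alone. With the last sample at 674 h it applies above 504/1.5 = 336 h, where extrapolation is 2^(−674/336) = 24.9%. Extrapolation reaches 30% at 674 × ln2/(−ln 0.3) = 388 h. Between 336 h and 388 h the literal text keeps AUC0-inf, CL, MRT and Vz in the tables.
- With samples to 1682 h, item 5 applies above 672/1.5 = 448 h, where extrapolation is only 2^(−1682/448) = 7.4%.

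**Step 4. Size of the error that could be retained (illustration).** Set the true rate and dose to 1, with a true extrapolated share e = 0.3, so tlast = −ln 0.3 = 1.204 and C(tlast) = 0.3. Infusion time is ignored. Suppose λz is estimated at 0.7.

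- AUC0-inf = 0.7 + 0.3/0.7 = 1.129 (+13%), so DNAUC0-inf is also +13%.
- Estimated extrapolation = (0.3/0.7)/1.129 = 38%, so the rule applies.
- AUMC to tlast = 1 − 0.3 × (1 + 1.204) = 0.339. The extrapolated part = 0.3 × 1.204/0.7 + 0.3/0.49 = 1.128. The total is 1.467.
- MRT = 1.467/1.129 = 1.300 (+30%); CL = 1/1.129 = 0.886 (−11%); Vss = 0.886 × 1.300 = 1.152 (+15%).

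A second case uses the projected AUC0-inf of 14000 µg·h/mL at 2 mg/kg (Protocol Table 3), a half-life of 335.1 h and a last sample at 338 h. An error of −30% or +30% in λz moves DNAUC0-inf from 7000 to 8491 or 6197, and Vss from 69.1 to 78.2 or 63.2 mL/kg. The extrapolation rule applies in every one of these cases.

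**The case against.** **The general wording covers the omitted parameters.** Each rule speaks of all dependent or all derived parameters, and by the SAP's own formulas Vss and DNAUC0-inf are such parameters. This is a fair reading. It means the fault in (b) is a list that conflicts with its own lead-in, so retention of Vss and DNAUC0-inf is possible but not certain. It does not settle the matter, because each lead-in is followed by a closed list (ie, not eg).

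**Item 5 is a drafting slip.** Its second sentence says the derived parameters are also flagged and excluded, with a footnoted reason, and the later text on listings ties flagging to exclusion from both tables and analysis. A slip is the likelier explanation. But that later text says excluded parameters will be flagged, not that flagged parameters are excluded from tables, so the literal gap remains.

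**The rules overlap.** In the 338 h profile, CL, MRT, Vz and AUC0-inf leave the tables through the extrapolation rule. This stands, and limits (a) mainly to half-life in that profile. Step 3 shows where the overlap ends.

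**The reach is small.** Vss and the dose-normalized AUCs are not in the protocol's endpoint list. AUC0-inf is excluded from statistical analysis under all three rules, so the dose-proportionality model is protected. Both points stand. The PK scientist's discretion could also repair a case, but it is written as a departure from the rule and does not replace a complete list.

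**Conclusion.** The inconsistency is real and minor. The firmer part is (a): followed literally, item 5 tabulates a half-life whose λz has been rejected, and also AUC0-inf, CL, MRT and Vz when extrapolation is within its limit. Part (b) is an ambiguity that could leave Vss and DNAUC0-inf in the summaries and boxplots.

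A reader might infer that unreliable clearance and volume values will be reported as a matter of course. The documents do not support that. The general wording can be read to exclude Vss and DNAUC0-inf, the extrapolation rule already removes CL in the truncated profile examined, and complete profiles to 1682 h trigger neither the 30% nor the 1.5-fold rule at the assumed half-lives.

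The effect is limited to truncated or irregular profiles or a longer half-life than assumed. Its frequency cannot be computed, because neither the LLOQ nor an expected dropout rate is given. The +15% for Vss and +13% for DNAUC0-inf rest on a chosen 30% error in λz and a mono-exponential decline; they illustrate the size and do not predict it.

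**What to change.** Reword SAP Table 5 before database lock:

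- **Extrapolation above the limit:** exclude %AUCex, AUC0-inf, DNAUC0-inf, CL, Vz, MRT and Vss.
- **Adjusted R² below 0.8, or interval below 1.5 half-lives:** exclude all of those plus λz and t1/2.
- **Scope, identical for all three rules:** flagged in listings, and excluded from summary tables, dose-normalized boxplots and statistical analysis.

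No new data or design change is needed. The cost is a slightly smaller n for the affected parameters in the summaries.
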